### 9.1 Severity

The severity of adverse changes in physical signs or symptoms will be classified as follows:

- Grade 1 (Mild): asymptomatic or mild symptoms; clinical or diagnostic observation only; intervention not indicated.
- Grade 2 (Moderate): minimal, local or noninvasive intervention indicated.
- Grade 3 (Severe): medically significant but not immediately life-threatening; hospitalization or prolongation of hospitalization indicated; disabling; limiting self-care/ADL.
- Grade 4 (Life-threatening): consequences; urgent intervention indicated.
- Grade 5 (Death): event is a direct cause of death.

### 9.2 Relatedness

- Definitely Related – There is clear evidence to suggest a causal relationship, and other possible contributing factors can be ruled out. The event cannot be explained by concurrent disease or other drugs or chemicals.
- Probably Related – There is evidence to suggest a causal relationship, and the influence of other factors is unlikely. The event occurs within a reasonable time after administration of the study protocol, is unlikely to be attributed to concurrent disease or other drugs or chemicals.
- Possibly Related – There is some evidence to suggest a causal relationship (e.g., the event occurred within a reasonable time after administration of study protocol). However, other factors may have contributed to the event (e.g., the participant's clinical condition, other concomitant events). Although an AE may rate only as "possibly related" soon after discovery, it can be flagged as requiring more information and later be upgraded to "probably related" or "definitely related", as appropriate.

- Unlikely to be related – An event whose temporal relationship to study protocol administration makes a causal relationship improbable (e.g., the event did not occur within a reasonable time after administration of the study protocol) and in which drugs, chemicals or underlying disease provides plausible explanations (e.g., the participant’s clinical condition, other concomitant treatments).
- Not Related – The AE is completely independent of study protocol administration, and/or evidence exists that the event is related to another etiology. There must be an alternative, definitive etiology documented by the clinician.

### **9.3 Expectedness**

The Principal Investigator will be responsible for determining whether an AE is expected or unexpected. An AE will be considered unexpected if the nature, severity, or frequency of the event is not consistent with the risk information previously described.

### **9.4 Reporting Serious Adverse Events**

Any SAE, which is determined by the PI to be unexpected and at least possibly related to study, will be reported to the IRB as soon as possible. The PI report to the IRB will include all known details regarding the nature of the SAE.

Life-threatening or fatal unexpected adverse events associated with the study procedures must be reported to the IRB within 24 hours of discovery of the incident with subsequent follow-up submission of a detailed written report in accordance with the respective policies and procedures of the IRB. Outcomes of SAEs will be regularly reported to the IRB. A summary of the SAEs that occurred during the previous year will be included in the annual progress report as well as in the annual IRB renewal.

#### **9.4.1 Adverse Events Reporting Timeline**

Life-threatening or fatal unexpected adverse events associated with the study must be reported to the IRB within 24 hours of discovery of the incident with subsequent follow-up submission of a detailed written report. The IRB will be notified by telephone or facsimile transmission of a human adverse event that is fatal or life-threatening no later than 7 calendar days after receiving the respective human adverse event information, followed by the subsequent submission of a written Safety Report. Serious and unexpected adverse events associated with the study protocol will be reported to the IRB with subsequent follow-up submission of a detailed written report in accordance with the respective policies and procedures of the IRB.

#### **9.4.2 Ensuring necessary medical/professional intervention for adverse events.**

If there is a suggestion that any research procedures have resulted in an injury to subjects, there will be immediate contact with the Principal Investigator who is listed on the first page of the informed consent documents. Emergency medical treatment for injuries solely and directly related to participation in this research study will be provided by the hospitals of UPMC. Insurance provider may be billed for the costs of this emergency treatment, but none of those costs will be charged directly to patients/subjects. If research-related injury requires medical care beyond this emergency treatment, subjects will be responsible for the costs of this follow-up care. Currently, there is no plan for any additional financial compensation for these events.

## **10 Withdrawal of Subjects and Stopping Rules**

### **10.1 Adverse Events Requiring Discontinuation**

For this study, a serious adverse event is any untoward clinical event that is thought by either the investigator or the sponsor to be related to the study and results in any of the following outcomes:

1. Death
2. A life-threatening adverse event
3. Inpatient hospitalization or prolongation of an existing hospitalization
4. A persistent or significant incapacity or substantial disruption of the ability to conduct normal life functions.
5. A congenital anomaly or birth defect
6. Important medical events that may not result in death, be life threatening, or require hospitalization may be considered serious when, based upon appropriate medical judgment, they may jeopardize the patient, or subject, and may require medical, or surgical intervention to prevent one of the serious outcomes listed above.

If clinically important and unexpected adverse experiences or clinically important study-related adverse experiences occur, they will be recorded on the adverse event case report form.

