## **7 Potential Risks and Benefits**

### **7.1 Reasonably Foreseeable Risks Related to Research**

*Risk associated with collecting and storing PHI.* Both common and infrequent risks include a loss of confidentiality.

*Risk associated with use of virtual reality devices.* No common risks are noted. Infrequent risks include the potential for patient to feel frustration, anxiety, or uncomfortable due to the device visualizations.

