#### **12 Data and Safety Monitoring**

[name] will be responsible for data and safety monitoring. She will meet bi-weekly with study personnel to review the progress of the research study, including subject recruitment and retention and an assessment of the timeliness and quality of the data. [name] will review all data, procedures, and any adverse events that occurred. All adverse events, including breach of confidentiality, will be reported to the IRB at minimum at the time of renewal per their policies and procedures.

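### The one stated rule for the adverse event form (Section 10.1) reaches only as far as clinically important experiences, a term left undefined; this conflicts with Sections 9.1 and 12, and mild device reactions need not be recorded

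*Combined protocol and SAP*

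**What the plan says.** Five sections bear on the point.

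- **Section 10.1** closes by stating that if "clinically important and unexpected adverse experiences or clinically important study-related adverse experiences occur, they will be recorded" on the adverse event case report form. No other sentence in the document says what goes on that form.
- **Section 7.1**, on the VR device: "Infrequent risks include the potential for patient to feel frustration, anxiety, or uncomfortable due to the device visualizations". It notes no common device risks.
- **Section 9.1** starts its severity scale at "Grade 1 (Mild): asymptomatic or mild symptoms; clinical or diagnostic observation only; intervention not indicated".
- **Section 9.3** defines expectedness: "An AE will be considered unexpected if the nature, severity, or frequency of the event is not consistent with the risk information previously described".
- **Section 12** says that the person responsible for monitoring "will review all data, procedures, and any adverse events that occurred", and that "All adverse events, including breach of confidentiality, will be reported to the IRB at minimum at the time of renewal".

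After the session, Section 6.2 repeats the STAI and EPDS and adds a feasibility questionnaire. The questionnaire items given in Section 11.1 concern ease of use, whether the session was worth the time, and willingness to take part again or regularly.

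**The concern.** Section 10.1 limits required recording to experiences that someone judges clinically important. Sections 9.1 and 12 are written as though adverse events of every grade are captured. A site following 10.1 as worded could leave a mild device reaction off the form and be compliant, and Section 12 would then have no record of it to review or report.

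This matters because of what the pilot is for. Its primary aim is feasibility and acceptability, its participants have a history of anxiety or depression, and Section 11.2 says it is to inform a fully powered trial. How well women tolerate the headset is part of that information. Anxiety is also both a named device risk and a treatment target. If the adverse event table is empty, a reader cannot tell whether no reactions occurred or whether some occurred and were judged not clinically important.

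**Working it through.** The plan states no figure on this point and no calculation applies. The check is to follow one event through the sections. Take a woman who feels brief, mild anxiety caused by the visualizations. That the episode is mild is an assumption of the example; Section 7.1 does not grade these reactions.

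1. **Is it a foreseen reaction?** Yes. Section 7.1 names anxiety from the visualizations.
2. **Can it be graded?** Yes. A mild symptom needing no intervention is Grade 1 under Section 9.1.
3. **Does it meet the first limb of 10.1 (clinically important and unexpected)?** Not if it occurs as described in 7.1, because 9.3 then makes it expected. A severity or frequency out of line with 7.1 would make it unexpected.
4. **Does it meet the second limb (clinically important and study-related)?** It is study-related, and this limb has no test of expectedness. The outcome depends wholly on whether it is clinically important.
5. **Is it clinically important?** The protocol gives no definition, so sites or staff may decide either way. An event whose grade is defined by needing no intervention is the kind most easily judged not to qualify.
6. **If it is judged not to qualify, what is required?** The sections diverge:

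| Section | Scope | Does it cover the example? |
|---|---|---|
| 9.1 | Severity grades from asymptomatic or mild upward | Yes, Grade 1 |
| 10.1 | Entry on the form for clinically important experiences | Entry not required |
| 12 | Review of any adverse event | Yes |
| 12 | IRB reporting of all adverse events, at minimum at renewal | Yes |

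The same event is gradable and reportable, yet has no required entry on the form that would carry it.

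7. **Would other data show it?** In part. A rise in anxiety could appear in the repeated STAI, but as an outcome score, not as an adverse event, and without attribution to the headset. Section 11.1 confines reporting to the number and proportion whose scores changed or decreased, so worsening need not be shown separately. The questionnaire items that 11.1 gives do not ask about frustration, discomfort or stopping early. Section 11 plans no adverse event summary.

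**The case against.** The strongest reply is that 10.1 sets a minimum, not a limit. It says that certain experiences will be recorded; it does not say that others will not be. It also closes a section about discontinuation, so it may never have been meant as the general collection rule. Sections 9.1 and 12 point to wider capture, and a site could reasonably treat device-induced anxiety as clinically important in women with this history. All of that stands. It shows that the protocol contradicts itself, not that it excludes these events. It does not remove the gap, because no other sentence governs the form.

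Several stronger readings are tempting and should not be drawn:

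- *That mild reactions can never reach the form.* The text contains no such exclusion, and a reaction judged clinically important and study-related must be recorded.
- *That reactions listed in 7.1 are excluded because they are expected.* The study-related limb has no expectedness test, so being listed excludes nothing.
- *That 7.1 gives the device's only risks, or calls them mild.* Its list is not stated to be complete, and it calls them infrequent.
- *That anxiety goes unobserved.* The STAI is given before and after the session. The full feasibility questionnaire is not reproduced, so its other items cannot be checked.
- *That this is the first use of the headset.* Section 2.1 says only that the effectiveness of VR for postpartum anxiety or depression has not been investigated.
- *That a confidence bound measures the damage.* Zero events in 6 women is compatible with a rate up to 1 − 0.05^(1/6) = 39% (one-sided 95% exact bound), and zero in 10 with up to 1 − 0.05^(1/10) = 26%. These bounds come from the sample size and would be the same with perfect recording.

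**Conclusion.** The concern holds as an internal inconsistency that can lead to under-recording. The only stated rule for the adverse event form depends in both limbs on an undefined judgement of clinical importance, while 9.1 grades milder events and 12 covers all adverse events. Mild occurrences of the reactions named in 7.1 therefore need not be recorded, and no described procedure asks about them as adverse events.

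The number of events lost cannot be estimated, because the documents give neither reaction rates nor what was in fact recorded. What can be said is how the result may be read: an empty adverse event table would speak to reactions judged clinically important, not to tolerability in general. In a sample of six, one unrecorded woman is 1/6 = 17%, which is context and not an estimate of loss.

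The conclusion assumes that staff apply 10.1 as written and that no separate instruction or questionnaire item, absent from these documents, fills the gap.

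**What to change.** **Protocol text.** Reconcile 10.1 with 9.1 and 12: adverse experiences of any grade, expected or not, are recorded on the form and graded under 9.1. Keep the narrower conditions (unexpected, related, serious) for expedited IRB reporting only.

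**Further participants and the full trial.** Add a short item to the existing post-session questionnaire asking about frustration, anxiety and discomfort during the session. Report the number of women with each, out of all who used the headset. That denominator is safer than completers, because Section 10.2 allows withdrawal for incomplete survey data.

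**The six women already completed.** Prospective questioning is no longer possible. State in the report that the written recording rule was limited to clinically important events and that no systematic questioning was specified. From existing data, give the number whose STAI worsened and the number whose EPDS worsened, beside the number who improved.

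**Cost.** One revised sentence, one short questionnaire item, a sentence of disclosure and two extra counts. The downside is a few more minor events to log.

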### **10.2 Other Criteria Requiring Discontinuation**

Withdrawal of Subjects for reasons other than Non-compliance or Adverse Events:

- Protocol non-adherence: non-adherence at follow-up visits at the judgement of the PI
- Incomplete survey data, defined as missing 20% or more responses

## **11 Statistical Analysis**

### **11.1 General Approach**

Baseline demographic characteristics will be collected and analyzed using descriptive statistics.

Feasibility of the study is measured as the number of patients who report that the study was both 1.) easy to use and 2.) The session was worth my time.

Acceptability was measured as “yes” responses to both questions, “would you participate in another session in the future? 2. Based on your experience today, would you participate in regular repeating sessions (e.g., daily, or weekly)?”

Anxiety and depression are measured as continuous variables at baseline and after VR intervention. Due to the small sample size, only the number (proportion) of patients whose overall anxiety and depression scores changed/decreased from baseline to post-intervention will be reported.

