## 1 Protocol Overview

Study Description	This project investigated whether a VR breathing intervention would reduce depression and anxiety symptoms in postpartum women with a history of depression and anxiety.
Study Population:	Six postpartum women with a history of anxiety or depression. All women were proficient in English reading and speaking.
Planned Sample Size:	10 women were anticipated to participate; 6 completed the study protocol
Participating Institutions (if a multi-center clinical trial)	University of Pittsburgh, UPMC Magee Women's Hospital

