#### **5.3 Exclusion Criteria**

- Unable to participate in study procedures.
- English illiterate

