#### VR Assessment:

The VR intervention consists of three key hardware components required for use. 1) a plastic Virtual Reality Headset (also known as HMD: Head Mounted Display), which covers a user’s eyes and is secured to their head using elastic straps which can be tightened with Velcro. The HMD houses a 2) smartphone which runs the Flowly software and renders stereoscopic images which are presented to the user through the HMD. The phone connects to 3) a Bluetooth heart rate monitor which gathers heart rate data and clips simultaneously to the user’s ear lobe using a spring-loaded clip and to their clothing.

The subject will download an app to their smartphone that will transmit data to Amazon Web Services managed by Tamade, LLC. Subjects will be lent an iPhone if they do not have an iPhone or version that can support the VR sessions. In the case that subjects do have an iPhone 6s/6s+ or higher (iPhone 6/6+ not eligible), they will be asked to use it for the completion of the study.

Subjects will be given the mobile system VR Shinecon head mounted display (HMD) and Bluetooth sensors to provide patients Virtual Reality biofeedback sessions targeted for depression/anxiety. While the participant is using the VR intervention, the following outcome measure will be gathered: pain level, heart rate, and respiration will be taken via the device and smartphone app and stored in a database hosted by Amazon Web Services and managed by Tamade, LLC.

Subjects will then complete in a 1-hour VR session. In terms of the experience of the VANISH intervention, most exercises focus on breathing. Users will see objects in a 3D virtual world which change movements with their breathing and the user will be guided to use these in manners that manage body responses. Breathing resonance variation will be collected from the subjects during these exercises using the VR device. Training on how to complete these breathing exercises will be initiated as a part of the device-training.

Follow-up Assessment:

To conclude, a post-assessment STAI and EPDS will be repeated, as well as post-assessment feasibility questionnaire.

The subjects will participate in a total of 2-hours to complete all questionnaires and the VR session.

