### **11.2 Sample Size Determination**

This is a sample of convenience as a pilot trial. We believe five complete subjects' answers will give us adequate information about feasibility and some estimations on measured outcomes to perform a sample size calculation for the fully powered trial.

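### Feasibility is counted only from two post-session opinions, with no denominator and no measure of whether sessions were started, completed or gave usable data

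*Combined protocol and SAP*

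**What the plan says.** The primary aim (Section 3.1.2) covers feasibility and acceptability. Section 11.3, on the primary endpoint, names feasibility alone and restates the aim without adding a measure.

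The only operative definition is in Section 11.1: "Feasibility of the study is measured as the number of patients who report that the study was both" easy to use and worth her time. This is a count. It has no denominator, success threshold or interval.

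Other sections decide who can contribute to that count:

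- **Entry (Section 5.3).** One exclusion criterion reads "Unable to participate in study procedures".
- **Timing (Section 6.2, Follow-up Assessment).** After the VR session the STAI and EPDS are repeated, "as well as post-assessment feasibility questionnaire".
- **Withdrawal (Section 10.2).** One criterion is "Incomplete survey data, defined as missing 20% or more responses".
- **Sample size (Section 11.2).** The study is a convenience sample, and the plan holds that "five complete subjects' answers will give us adequate information about feasibility" and will support a sample size calculation for a fully powered trial.

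Section 1 states that "10 women were anticipated to participate; 6 completed the study protocol". Recruitment and retention appear in Section 12 as topics for the bi-weekly review, "including subject recruitment and retention and an assessment of the timeliness and quality of the data", and again in Section 13.3 as topics for weekly team meetings. Neither section makes them an endpoint.

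**The concern.** A pilot that is meant to prepare a powered trial should show whether the procedure can be delivered. Section 6.2 describes several steps at which delivery can fail: a compatible or loaned phone, an app download, a headset, a Bluetooth ear sensor and transmission to a hosted database. The feasibility measure records none of them. It asks for an opinion at the end, when women for whom a step failed are the least likely to be answering.

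The later trial also needs a completion rate and a usable-data rate to set its recruitment target. The count in Section 11.1 yields neither, and without a denominator readers may take it as a proportion of whichever group they assume.

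**Working it through.** **Inputs**

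| Input | Value | Source |
|---|---|---|
| Women anticipated | 10 | Section 1 |
| Women who completed | 6 | Sections 1 and 5.1 |
| Complete subjects judged adequate | 5 | Section 11.2 |
| Women approached, consented, started | not stated | – |
| Denominator or success threshold for feasibility | not stated | Sections 11.1, 11.3 |

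The plan has no calculated figure to reproduce, because Section 11.2 gives no rate, precision target or dropout allowance.

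**Step 1: who answers.** The items come after the session, heavily incomplete survey data is a withdrawal criterion, and Section 11.2 relies on complete subjects. Together these leave the women who finished as the natural responders.

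**Step 2: best result among responders.** Suppose all six endorse both items. The proportion is 6/6 = 100%. For x = n the exact (Clopper-Pearson) 95% lower limit is (0.025)^(1/n):

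(0.025)^(1/6) = 0.541

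The interval is 54.1% to 100%. If five of six endorse both, the proportion is 83.3% (exact 95% CI 35.9% to 99.6%).

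**Step 3: the same six answers over all consented women.** Let N be the number consented, assumed to lie between 6 and 10, with non-responders counted as not endorsing. The result is 6/N.

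| N consented (assumed) | Count under Section 11.1 | 6/N |
|---|---|---|
| 6 | 6 | 100% |
| 7 | 6 | 86% |
| 8 | 6 | 75% |
| 9 | 6 | 67% |
| 10 | 6 | 60% |

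The second column does not change. A study in which six women consented and all finished, and one in which ten consented and four were lost, give the same feasibility result. The range that the definition cannot show is 100 − 60 = 40 percentage points.

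The table gives no intervals because N is assumed. An interval on 6 out of the 10 anticipated would have no sampling meaning, since 10 is a plan and not a set of women observed.

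**Step 4: can completion be defined now?** The Section 6 summary describes a 30-minute VR session; Section 6.2 describes a 1-hour session. Until these are reconciled, a completed session has no agreed meaning.

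**The case against.** The sponsor has several fair replies.

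- **The construct.** Sections 3.1.2 and 11.3 concern feasibility of using VR, and Section 3.1.1 asks whether it is feasible as a management tool. Ease of use bears directly on that. This stands: it would be wrong to dismiss both items as mere acceptability. But Section 11.1 speaks of feasibility of the study and Section 11.2 looks ahead to a powered trial, so a broader measure is needed beside the two items.
- **The count.** Section 11.1 defines a number, and a number falls when fewer women take part. This also stands. A reader might infer that a study which failed to recruit or deliver would still be declared feasible. The plan sets no threshold, so no such declaration is defined. The defect is the missing denominator and missing delivery measures.
- **Early stoppers.** A reader might infer that women who stop can never answer the questionnaire. No section bars them from doing so, nor does the plan say whether a withdrawn woman's answers are discarded. That the result rests on finishers is a practical expectation from the timing and withdrawal rules.
- **Timing.** Version 2.0 (September 2023) already reports six completers. Replacing the primary measure now would redefine it after data collection. This stands and limits the remedy to additions.
- **Records.** Sections 6.1 and 13.2 say that record-review information on ineligible women is destroyed immediately, and no log of women approached is described. Approach and exclusion counts may therefore not exist.

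**Conclusion.** The point holds as a gap in the definition and reporting of feasibility. The stated measure cannot show failure to start or finish sessions, or to obtain usable data, and it lacks a denominator.

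If all six completers endorse both items, the result is 6/6 (exact 95% CI 54% to 100%). Over all consented women the same answers could mean anything from 100% to 60%. That range assumes 6 to 10 women consented and that non-responders count as not endorsing; the documents confirm neither.

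A tempting stronger reading is that 4 of 10 women dropped out, or that completion was 60%. The documents do not support it. Ten is the number anticipated, and the gap of four may be under-recruitment, dropout or both. Completion among consented women could have been 100%.

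The matter should be corrected before the pilot is used to plan a larger trial. It raises no safety issue.

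**What to change.** In Sections 11.1 and 11.3:

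1. Keep the two existing items. Report the number endorsing both over all consented women, counting non-responders as not endorsing.
2. Beside them report four counts, each over all consented women with an exact 95% interval: session started, session completed, app sensor data captured, and usable pre and post questionnaires.
3. Label the four counts and the chosen denominator as added after data collection.
4. Give numbers approached or excluded (including those excluded as unable to take part) only if they were recorded; otherwise state that they are unavailable.
5. Reconcile the session length in the Section 6 summary with that in Section 6.2, then define a completed session.
6. Do not present 6 of the 10 anticipated as a completion rate or attach an interval to it.

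The cost is a small flow table and a few lines of text. The sources should already exist: signed consent forms (Section 13.1), app-stored session data and questionnaires (Section 6.2), and the deviation log (Section 13.3). No new contact with participants is needed. The drawback is that the reported figure may be less favourable.

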##### **3.1.3 Secondary Aim:**

To identify changes in depression and anxiety from baseline to post treatment.

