### **5 Human Subjects**

#### **5.1 Subject Population**

Six postpartum women with a history of anxiety or depression participated in a single VR biofeedback session.

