### **11.3 Analysis of Primary Endpoint**

To explore the feasibility of use of Virtual Reality as a method to aid in the reduction of anxiety and depression in postpartum women.

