#### **11.4 Analysis of Secondary Endpoint**

To further explore change in anxiety and depression across the trials.

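### Section 11.1 reduces the EPDS and STAI change to a loosely defined count of women, so the planned report shows neither the size nor the spread of change

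*Combined protocol and SAP*

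**What the plan says.** The secondary aim in Section 3.1.3 is "To identify changes in depression and anxiety from baseline to post treatment". Section 11.1 states the measurement scale: "Anxiety and depression are measured as continuous variables at baseline and after VR intervention". The next sentence gives the small sample as the reason for a restriction, under which "only the number (proportion) of patients whose overall anxiety and depression scores changed/decreased from baseline to post-intervention will be reported".

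Section 11.4, headed as the analysis of the secondary endpoint, says "To further explore change in anxiety and depression across the trials" and names no statistic. Section 11.1 plans descriptive statistics for baseline demographic characteristics only. No section plans a mean, median, SD, range or individual listing of EPDS or STAI change.

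On direction, Section 11.3 describes VR "as a method to aid in the reduction of anxiety and depression in postpartum women". The study description in Section 1 and the rationale in Section 2.2 also speak of reducing symptoms. Sections 6 and 6.2 name the State-Trait Anxiety Inventory without saying whether the state, trait or total score is used. Section 1 records that six women completed, against ten anticipated.

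**The concern.** A change on a continuous scale has a direction, a size and a spread. The planned report keeps at most the direction. A reader could not tell a one-point shift from an eight-point shift, and would have no measure of how much the women differed.

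The count also cannot be reproduced from the wording alone, for three reasons:

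- *Changed* includes a woman who worsens; *decreased* does not.
- Naming anxiety and depression together allows one count per scale or one joint count.
- *Overall* anxiety does not identify a STAI score.

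Two analysts following Section 11.1 could report different numbers from the same six women. At stake is how well the secondary aim is answered.

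**Working it through.** The plan gives no figure for this outcome that could be reproduced, and no EPDS or STAI values. All score changes below are assumed, for illustration. The only document input is n = 6 completers (Section 1).

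**1. Same count, different change.** Take two sets of six paired changes (post minus pre):

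- A: -1, -1, -2, -1, +1, -1
- B: -8, -6, -12, -3, +5, -9

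| | A | B |
|---|---|---|
| Decreased / unchanged / increased | 5 / 0 / 1 | 5 / 0 / 1 |
| Changed | 6/6 | 6/6 |
| Median | -1 | -7 |
| Range | -2 to 1 | -12 to 5 |
| Mean | -5/6 = -0.83 | -33/6 = -5.50 |
| SD | sqrt(4.833/5) = 0.98 | sqrt(177.5/5) = 5.96 |

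The Section 11.1 summary is identical for both sets. The ratio of mean to SD is similar (-0.85 and -0.92), so what the count hides here is the size in score points and the SD, not the standardised change.

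**2. Same data, different count.** Let the EPDS changes be set B and let the changes on some STAI score, for the same women in the same order, be -4, +3, -7, -2, -5, -6.

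- Decreased on EPDS: women 1, 2, 3, 4, 6, so 5/6.
- Decreased on STAI: women 1, 3, 4, 5, 6, so 5/6.
- Decreased on both: women 1, 3, 4, 6, so 4/6.
- Changed, on either scale or on both: 6/6.

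The reported figure is 4/6, 5/6 or 6/6 according to the reading. A different STAI score could alter it again.

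**3. Does counting avoid the small-sample problem?** Exact (Clopper-Pearson) 95% intervals:

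- 5/6: the lower limit solves 6p^5(1-p) + p^6 = 0.025, giving 0.359; the upper limit is 0.975^(1/6) = 0.996.
- 4/6: 0.223 to 0.957.
- 6/6: 0.025^(1/6) = 0.541, up to 1.

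The proportion is as exposed to the small n as any other summary.

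**4. Precision of the fuller description at n = 6, assuming normality.**

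- 95% limits for the SD are the observed SD times sqrt(5/chi-square quantile on 5 df): 0.62 to 2.45 times.
- The t-based 95% half-width for the mean is t/sqrt(6) = 1.05 SD.

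These summaries are very imprecise, but they do convey size and spread.

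**The case against.** The restriction is deliberate, and the plan gives its reason. With about six women in an uncontrolled convenience pilot, who "participated in a single VR biofeedback session", reporting counts on a secondary aim is defensible. Means and intervals at this size invite over-reading. In particular, a t-based 95% interval for mean change can be read as a test against zero, and its normality assumption cannot be verified with six scores. That part stands, so the interval should be optional at most. It does not justify leaving out a plain description of change, which involves no test and which the count does not replace.

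The looseness on direction can also be overstated. Sections 1, 2.2 and 11.3 all point to reduction, so *decreased* is the likelier reading, and the eventual report could simply label its count. This narrows the ambiguity, but Section 11.1 does not state it. Separate or joint counting and the choice of STAI score are settled nowhere.

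A reader might further infer that Section 11.1 contradicts Section 11.2, which expects "some estimations on measured outcomes to perform a sample size calculation for the fully powered trial". The documents do not support that. Section 11.1 limits what is reported, while the raw scores remain available to the team for planning. Taking the measured outcomes to mean EPDS and STAI is itself an inference: Section 6.2 says that "the following outcome measure will be gathered: pain level, heart rate, and respiration will be taken via the device and smartphone app", and the later trial's endpoint is not stated.

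**Conclusion.** The point holds as a gap in the planned report of a secondary, descriptive outcome. Followed as written, Section 11.1 could present median changes of -1 and -7 points as the same 5/6, and could give 4/6, 5/6 or 6/6 from a single data set. The stated reason, small numbers, supports avoiding hypothesis tests but not omitting size and spread.

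The illustrations rest on assumed score changes. They show what the count can conceal, not what happened in these six women. It would go too far to conclude that the data are inadequate, that later sizing is impossible, or that the primary results are compromised. The continuous scores are collected, and the feasibility and acceptability measures do not depend on them. This is a cheap improvement that should be made, at the low end of priority.

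**What to change.** Keep the existing Section 11.1 sentence on record. Add a dated supplement to Sections 11.1 and 11.4, labelled post hoc because six women have already completed, along these lines:

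> For EPDS and for the named STAI score(s), separately, the median and range of the paired change, with mean and SD, will be reported descriptively without a hypothesis test. For each scale, the numbers of women whose score decreased, was unchanged or increased will be given, with the number of women with both scores as the denominator.

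The supplement must name the STAI score or scores: state, trait or total. Stating the denominator matters because Section 10.2 withdraws women who miss 20% or more of survey responses. A t-based 95% interval for the mean is optional; if given, it should be labelled as resting on a normality assumption that cannot be verified here. Section 11.2 needs no change.

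The cost is a few lines of analysis on scores already collected. There are three downsides: the summaries will be very imprecise, the additions carry a post hoc label, and the range discloses two individual change values, so it needs a brief check against the confidentiality commitments in Section 8.1.
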